10.3 Method of Assigning Subjects to Treatment Groups

Approximately 490 subjects who meet the eligibility criteria will be randomized (1:1) to 1 of 2 treatment arms. Randomization will be stratified by age at the Screening Visit (<18 versus \geq 18 years of age), sex (male versus female), and FEV₁ severity collected during the Screening Period (<70% versus \geq 70% predicted).

An interactive web response system (IWRS) will be used to assign subjects to treatment. Detailed instructions for randomization will be provided separately.

10.4 Dose Modification for Toxicity

The dosage of VX-661 or ivacaftor cannot be altered, but the investigator can interrupt or stop treatment.

10.5 Study Drug Interruption

If study drug dosing must be interrupted for more than 72 hours, the medical monitor must be notified. In these instances, study drug dosing may only resume after approval by the medical monitor. Specific instructions for interruption for elevated LFT levels and elevated QTc levels are provided in Section 11.7.7 and Section 11.7.4, respectively.

10.6 Missed Doses

If a subject misses a dose and recalls the missed dose within 6 hours, the subject should take his/her dose with food. If more than 6 hours have elapsed after his/her usual dosing time, the subject should skip that dose and resume his/her normal schedule for the following dose. For example,

- if the morning dose of study drug should have been taken at approximately 08:00, and the subject remembers at 12:00 that he/she forgot to take his/her dose, he/she should take the dose with food as soon as possible.
- if the morning dose of study drug should have been taken at approximately 08:00, and more than 6 hours have elapsed beyond the scheduled dosing time (i.e., the time is past 14:00), the subject would resume dosing with the evening dose at approximately 20:00.

10.7 Packaging and Labeling

Study drug tablets will be supplied in blister cards by Vertex. Study drug cards will be provided and replaced via the IWRS. A detailed study drug dispensation plan will be provided in the Pharmacy Manual.

Study drug labeling will be in compliance with applicable local and national regulations.

10.8 Study Drug Supply, Storage, and Handling

VX-661/ivacaftor (100 mg/150 mg) and matching placebo will be supplied as light yellow film-coated tablets of similar size and appearance containing 100 mg VX-661/150 mg ivacaftor and 0 mg VX-661/0 mg ivacaftor, respectively.

Ivacaftor (150 mg) and matching placebo will be supplied as light blue film-coated tablets of similar size and appearance containing 150 mg ivacaftor and 0 mg ivacaftor, respectively.

Blister cards must be stored at room temperature according to Table 10-2 and to the instructions provided in the Pharmacy Manual. The investigator, or an authorized designee (e.g., a licensed pharmacist), will ensure that all investigational product is stored in a secured area, under recommended study conditions, and in accordance with applicable regulatory requirements. To ensure adequate records, all study drugs will be accounted for as detailed in Section 10.9.

Instructions regarding the storage and handling of study drug after dispensation to subjects will be provided to sites in the Pharmacy Manual.

Table 10-2 Identity of Study Drugs, Dosage, and Storage

Drug Name	Strength/Formulation/Route	Dosage	Storage Condition
VX-661/ivacaftor fixed-dose tablet	100-mg/150-mg tablet; oral	100 mg/ 150 mg, morning dose	≤ 25°C (77°F) with excursions to 30°C (86°F)
Ivacaftor	150-mg tablet, oral	150 mg, evening dose	≤ 25°C (77°F) with excursions to 30°C (86°F)
VX-661/ivacaftor matching placebo	0-mg/0-mg tablet; oral	0 mg/ 0 mg morning dose	≤ 25°C (77°F) with excursions to 30°C (86°F)
Ivacaftor, matching placebo	0-mg tablet, oral	0 mg, evening dose	≤ 25°C (77°F) with excursions to 30°C (86°F)

10.9 Drug Accountability

The pharmacist or designated site staff will maintain records documenting the dates and amounts of

- study drug received,
- study drug dispensed to the subjects, and
- study drug returned by the subjects.

Subjects will be instructed to return all used, partially used, and full study drug blister cards to the site. These materials will be retained at the site according to instructions provided by Vertex or its designee until inventoried by the study monitor. The study monitor will verify study drug records and inventory throughout the study.

10.10 Disposal, Return, or Retention of Unused Drug

The site staff or pharmacy personnel will retain all materials returned by the subjects until the site monitor has performed drug accountability. At the end of the study, the study monitor will provide instructions as to the disposition of any unused investigational product. If the study monitor authorizes destruction at the study site, the investigator will ensure that the materials are destroyed in compliance with applicable environmental regulations, institutional policy, and any special instructions provided by Vertex. Destruction will be adequately documented.

Procedures for destruction or return of the study drug will be detailed in the Pharmacy Manual.

10.11 Compliance

To ensure treatment compliance, the investigator or designee will supervise all study drug dosing that occurs at the site. At each visit, site personnel will review that the subject is compliant with study drug dosing and remind the subject of study drug dosing requirements. Compliance will also be assessed by ongoing study drug count.

If a subject demonstrates continued noncompliance of study drug dosing despite educational efforts, the investigator should contact the medical monitor to discuss discontinuation of the subject from the study treatment.

10.12 Blinding and Unblinding

This is a double-blind study.

10.12.1 Blinding

The subjects and all site personnel, including the investigator, the site monitor, and the study team, will be blinded with the exception of the following:

- Any site personnel for whom this information is important to ensure the safety of the subject in the event of a life-threatening medical emergency
- Any site personnel for whom this information is important to ensure the safety of the subject and their fetus in the event of a pregnancy
- Vertex Global Patient Safety (GPS) and Regulatory Affairs personnel to satisfy SAE processing and reporting regulations
- Unblinded statistician preparing the final (production) randomization list who is not part of the study team
- Vertex Clinical Operations IWRS management
- Vertex Clinical Supply Chain
- IDMC
- Vendor preparing the unblinded analysis for the IDMC
- Vendor analyzing PK samples
- Vertex or vendor conducting the population PK analysis
- Vertex medical monitor may, for matters relating to safety concerns, unblind individual subjects at any time

Vertex Drug Metabolism and Pharmacokinetics laboratory personnel will not be involved in the conduct of the study and will be unblinded to the bioanalysis results but will remain blinded to subject number and treatment assignment.

Spirometry Data Blinding

Despite treatment blinding, knowledge of the spirometry results has the potential to suggest whether a subject has been administered active study drug or placebo. Therefore, during the conduct of the study, the Vertex study team will have no access to the postdose spirometry

data. The vendor for central reading of the spirometry data will only send the blinded spirometry files (blinded treatment group, with real values for screening and baseline, but with dummy values for all the spirometry assessment after baseline) to Vertex to be used for developing the statistical programs. Furthermore, subjects and their caregiver should not be informed of their study-related spirometry results during the Treatment Period regardless of whether the subject has prematurely discontinued treatment.

Sweat Chloride Data Blinding

Despite treatment blinding, knowledge of the sweat chloride data has the potential to suggest whether a subject has been administered active study drug or placebo. Therefore, during the conduct of the study, the Vertex study team will have no access to the postdose sweat chloride data; dummy data will be used to develop statistical programs. During the process of locking the clinical database, after all study visits have been completed, access to treatment-blinded sweat chloride data will be provided to a small group of individuals (a biostatistician, a statistical programmer, a validation statistical programmer, and a clinical reviewer) who are not part of the Vertex study team. This small group will review the sweat chloride data to ensure there are no significant data issues and will use the blinded data set to refine the statistical programs.

10.12.2 Unblinding

At the initiation of the study, the study site will be instructed on the method for breaking the blind. The unblinding method will be either a manual or electronic process.

Unblinding of the individual subject's treatment by the investigator will be limited to medical emergencies or urgent clinical situations in which knowledge of the subject's study treatment is necessary for clinical management. In such cases, investigators should use their best judgment as to whether to unblind without first attempting to contact the medical monitor to discuss and agree to the need for unblinding. If investigators deem that it is not necessary to unblind immediately, they will first attempt to contact the medical monitor to discuss and agree to the need for unblinding. If investigators have tried but are unable to reach the medical monitor, they should use their best judgment, based on the nature and urgency of the clinical situation, and may proceed with unblinding without having successfully reached and discussed the situation with the medical monitor.

Contact information for the medical monitor (or appropriate backup) will be provided in a separate document.

In addition, the Vertex Medical Information Call Center [REDACTED] will answer calls 24 hours a day, 7 days a week, 365 days of the year, and will triage these calls to the study medical monitor or appropriate backup.

If a subject's treatment assignment has been unblinded for a medical emergency or urgent clinical situation, the medical monitor should be notified within 24 hours of the unblinding event. The reason and the date of the unblinding will be documented clearly in the subject's study file. Information about the treatment assignment obtained from the unblinding will be maintained in a secure location with controlled access and will not be shared with sponsor (Vertex), contract research organization (CRO), or any site personnel (other than the physician treating the subject). In addition, the investigator will consider whether the clinical

event that prompted unblinding will be considered an SAE, according to the regulatory definitions or criteria for SAEs, and if so, submit an SAE report to Vertex GPS or designee, per Section 13.1.2.

Vertex GPS or designee will also unblind any SAE reports in compliance with regulatory reporting requirements. In addition, the Vertex medical monitor may, for matters relating to safety concerns, unblind individual subjects at any time.

11 ASSESSMENTS

11.1 Timing of Assessments

The timing of assessments is shown in Table 3-1 and Table 3-2.

The CFQ-R questionnaire must be performed before any other assessment at the clinic visits when it is required. For the remaining assessments, the following assessments must be performed in the following order when more than 1 assessment is required at a particular time point:

██████████

████████████████████

██████████

4. standard 12-lead ECG recordings
5. vital signs and pulse oximetry
6. spirometry
7. sweat chloride
8. safety laboratory assessments (i.e., blood draws)
9. PK sampling

Note: if study drug is not administered on the day of the visit (for any reason, including study drug interruption or premature discontinuation of study drug), only 1 set of assessments will be collected (Table 3-2).

11.1.1 Informed Consent/Assent

Each subject of age of consent (per local requirements) must sign and date a study-specific ICF before any study-specific procedures can be performed. Subjects not of age of consent must assent, if applicable per local requirements, to participate in the study, and the subject's parent or legal guardian must sign and date a study-specific ICF before any study-specific procedures can be performed. The consent forms will comply with all applicable regulations governing the protection of human subjects. An ICF and Assent Form, approved by Vertex and the site's institutional review board (IRB) or ethics committee (EC), must be used.

11.1.2 Assigning Subject Number

Once a subject has signed an ICF or assent, if applicable, a subject number will be assigned. The subject will retain this number for the entire study. Detailed instructions on assigning

subject numbers will be provided in the Study Reference Manual. If a subject is rescreened, the subject retains the original subject number.

11.2 Subject and Disease Characteristics

Subject and disease characteristics include the following: demographics, medical history, height, and weight.

Medical history will be elicited from each subject during screening. Based on the medical history, the subject will be assessed for any disqualifying medical conditions as specified in the inclusion and exclusion criteria. The medical history shall include a complete review of systems, past medical and surgical histories, and any allergies.

11.3 Total Blood Volume

Total blood volume will be outlined in the Laboratory Manual.

11.4 Pharmacokinetics

11.4.1 Blood Sampling

Blood samples will be collected as shown in Table 3-1 and Table 3-2.

At the visits and time points indicated in Table 3-2, blood samples will be collected for the determination of the concentrations of VX-661, M1-661, M2-661, ivacaftor, and M1-ivacaftor. Blood samples collected before dosing must be collected within 60 minutes before dosing. The acceptable windows for PK sampling time points are detailed in Table 11-1.

Samples from the PK sampling will be kept frozen by Vertex or its designee until all analyses have been completed and then disposed of according to Vertex or designee standard operating procedures.

For each visit with a PK blood draw, a record of study drug administration will be collected as described in Section 10.2. The collection date and time that each PK blood sample is drawn will also be recorded.

Details on sample collection, processing, and shipping will be provided in a separate protocol-specific Laboratory Manual.

Table 11-1 Acceptable Pharmacokinetic Sampling Windows

Sampling time	Time From Sampling Schedule Allowed
Predose	Within 60 minutes before study drug dose on the PK sampling date
0.5 hours after study drug dosing	± 10 minutes
2, 3, 4, 6, and 8 hours after study drug dosing	± 30 minutes

11.4.2 Processing and Handling of Pharmacokinetic Samples

Detailed procedures for the collection of blood samples, and further procedures for processing and handling of samples for PK analysis, will be provided in the Laboratory Manual. The shipment address and assay laboratory contact information will be provided to the investigational site before initiation of the study.

11.4.3 Bioanalysis

Samples will be analyzed using a validated analytical method in compliance with Vertex or designee standard operating procedures. A description of the assay methods and validation data will be provided in separate reports.

If appropriate, these samples may also be used for evaluations of metabolites of VX-661 and ivacaftor during treatment. These samples may also be used for further evaluation of the bioanalytical method and for analyses that provide information on the metabolic pathways used or impacted by VX-661 and ivacaftor. These data will be used for exploratory purposes and may not be included in the clinical study report.

[REDACTED]

11.6 Efficacy

11.6.1 Spirometry

Spirometry will be performed according to the American Thoracic Society Guidelines⁴⁰ at the time points noted in Table 3-1 and Table 3-2 according to the additional guidelines that follow.

Prebronchodilator spirometry is defined as spirometry testing performed for subjects who have

- withheld their short-acting bronchodilators (e.g., albuterol) or anticholinergic (e.g., ipratropium bromide [Atrovent[®]]) for more than 4 hours before the spirometry assessment;
- withheld their long-acting bronchodilator (e.g., salmeterol) for more than 12 hours before the spirometry assessment; and
- withheld their once-daily, long-acting bronchodilator (e.g., tiotropium bromide [Spiriva[®]]) for more than 24 hours before the spirometry assessment.

During the Treatment Period, spirometry assessments must be performed before dosing. In adolescent subjects (<18 years of age at the Screening Visit) additional postdose spirometry assessments on Day 1 and Day 15 will be collected.

During the Screening Period, spirometry assessments may be performed pre- or postbronchodilator. At all other visits, all spirometry assessments should be performed "prebronchodilator." In the event that a subject forgets or is unable to withhold bronchodilator(s), spirometry should be performed according to the following:

- If a subject's Day 1 spirometry is prebronchodilator, but, on a subsequent visit, the subject does not withhold bronchodilator use, a postbronchodilator spirometry will be obtained for that visit only, and the visit will not be rescheduled.
- If, on Day 1, the subject does not withhold his/her dose of bronchodilator, spirometry should be performed postbronchodilator, and all subsequent spirometric measurements (according to the schedule of assessments detailed in Table 3-2) should be performed postbronchodilator.
- Spirometry assessments that occur after dosing (postdose) on Day 1 and Day 15 (for subjects <18 years of age) should be performed prebronchodilator. If Day 1 and/or Day 15 predose spirometry is performed postbronchodilator, the subject should withhold any further bronchodilator use until after completion of the 4-hour postdose spirometry.
- Each spirometry assessment will be recorded in the source documents as pre- or postbronchodilator.

All sites will be provided with spirometers to be used for all study assessment. Spirometry data will be transmitted to a centralized spirometry service for quality review.

Subjects and their parent/caregiver should not be informed of their study-related spirometry results during the Treatment Period (Day 1 through Week 24), regardless of whether the subject prematurely discontinues treatment.

The parameters listed below will be normalized using the standards of Wang et al⁴¹ (for female subjects aged 12 to 15 years [inclusive] and male subjects aged 12 to 17 years [inclusive]) or Hankinson et al⁴² (for female subjects aged 16 years and older and male subjects aged 18 years and older).

- FEV₁ (L)
- Forced vital capacity (FVC) (L)
- FEV₁/FVC (ratio)
- Forced expiratory flow (FEF_{25%-75%}) (L/s)

11.6.2 Sweat Chloride Testing

The sweat chloride test is a standard diagnostic tool for CF, serving as a biomarker of CFTR activity. Collection of sweat samples will be performed at visits specified in Table 3-1 and Table 3-2, using an approved collection device. Sweat samples will be sent to a central laboratory for testing and interpretation of results. Individual sweat chloride test results will not be disclosed to the study sites. Specific instructions for collection, handling, processing, and shipping of sweat chloride samples to the central laboratory will be provided separately.

The sweat chloride collection on Day 1, Week 4, Week 16, and Week 24 will occur approximately 1 hour before the PK sample collection and before the morning dose of the study drugs. At each time point, 2 samples will be collected, 1 from each arm (left and right). Additionally, sweat collection will be performed at the Screening Visit and ETT Visit. Collection of sweat chloride will not overlap with any other study assessments.

11.6.3 Height and Weight

Height and weight will be measured with shoes off at time points noted in Table 3-1 and Table 3-2. Height and weight will be measured before the morning dose of the study drug during the Treatment Period. During the Treatment Period and at the Safety Follow-up Visit, height will be collected only for subjects 21 years of age or younger.

11.6.4 Cystic Fibrosis Questionnaire-Revised

Subjects will be asked to complete the CFQ-R in their native language. The CFQ-R will be completed before the start of any other assessments, as noted in Table 3-1 and Table 3-2. Subjects who are 12 and 13 years of age at Day 1 will complete the CFQ-R Child version themselves, and their parents/caregivers will complete the CFQ-R Parent version, on all visits, regardless of whether the subject subsequently turns 14 years of age during the study. Subjects 14 years of age and older at Day 1 will complete the Adolescent/Adult version of the questionnaire themselves at all visits. The questionnaires provide information about demographics; general quality of life, school, work, or daily activities; and symptom difficulties (pertaining to CF). Copies of the CFQ-R used in this study will be provided in the Study Reference Manual. Validated translations^{26,27} of the CFQ-R, if available, will be provided for participating centers in non-English-speaking countries.

11.6.12 Other Events Related to Outcome

11.6.12.1 Antibiotic Therapy for Sinopulmonary Sign/Symptoms

New or changed antibiotic therapy (IV, inhaled, or oral) for the following sinopulmonary signs/symptoms will be determined and documented at visits as indicated in Table 3-2:

- Change in sputum
- New or increased hemoptysis
- Increased cough
- Increased dyspnea
- Malaise, fatigue, or lethargy
- Temperature above 38°C (equivalent to approximately 100.4°F)
- Anorexia or weight loss
- Sinus pain or tenderness
- Change in sinus discharge
- Change in physical examination (PE) of the chest
- Decrease in pulmonary function by 10%
- Radiographic changes indicative of pulmonary infection

For this study, pulmonary exacerbation is defined as a new event or change in antibiotic therapy (IV, inhaled, or oral) for any 4 or more of the above signs/symptoms. This definition is based on the definition of a pulmonary exacerbation used in previous clinical studies including ivacaftor clinical studies.^{31,43}

It is recommended that the study drug should not be interrupted during a pulmonary exacerbation unless, in the opinion of the investigator, it would be in the best interest of the subject.

The following information will be determined for protocol-defined pulmonary exacerbations:

- Number of pulmonary exacerbations
- Number of days with pulmonary exacerbations
- Time-to-first pulmonary exacerbation
- Number of pulmonary exacerbations requiring hospitalizations
- Number of days hospitalized for pulmonary exacerbations*

- Time-to-first hospitalization for pulmonary exacerbation
- Number of pulmonary exacerbations requiring IV antibiotic therapy
- Number of days on IV antibiotic therapy for pulmonary exacerbations
- Time-to-first IV antibiotic therapy for pulmonary exacerbations

*For each treatment group, the number of days hospitalized for pulmonary exacerbations will be analyzed as 48 weeks times the total numbers of days in hospital for pulmonary exacerbation, divided by the total number of weeks on-treatment, for all subjects in the same treatment group.

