8.1.2 Treatment Period (Day 1 Through Week 24)

The Treatment Period will last approximately 24 weeks. Subjects will be randomized to 1 of 2 treatment arms: 1 combination treatment arm and 1 placebo arm. The dosing regimen for each treatment arm is shown in Figure 8-1 and is as follows:

- VX-661/ivacaftor: 100-mg VX-661/150-mg ivacaftor fixed-dose combination (light yellow) film-coated tablet for oral administration (morning dose); 150-mg ivacaftor (light blue) film-coated tablet for oral administration (evening dose)
- Placebo: 0-mg film-coated matching placebo tablets for oral administration (1 light yellow for morning dose and 1 light blue for evening dose)

The first dose of the study drug will be administered after randomization on Day 1. Dosing details are given in Section 10.2.

Study visits during the Treatment Period will occur as shown in Table 3-2. Subjects will be outpatients during the Treatment Period. All visits should occur within the windows specified.

Subjects who prematurely discontinue study drug treatment will remain in the study from the time of discontinuation of study drug treatment through the Week 24 Visit and complete assessments for all study visits, as described in Section 8.1.4.

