8.1.4 Early Treatment Termination

If the subject prematurely discontinues study treatment, an Early Treatment Termination Visit should be scheduled as soon as possible after the subject decides to terminate study treatment. Subjects who prematurely discontinue treatment will also be required to complete the Safety Follow-up Visit, approximately 28 (\pm 7) days after their last dose of study drug. The assessments performed at the Safety Follow-up Visit are listed in Table 3-2.

If the Early Treatment Termination Visit occurs 3 weeks or later following the last dose of study drug, then the Early Treatment Termination Visit will replace the Safety Follow-up Visit, and a separate Safety Follow-up Visit will not be required.

Subjects will continue to complete all other scheduled study visits for assessments of efficacy (spirometry, CFQ-R, sweat chloride, height, and weight), [REDACTED], and other events related to outcome (hospitalizations, pulmonary exacerbations, etc.) as detailed in the Schedules of Assessments (Section 3).

If the subject withdraws from the study and also withdraws consent for disclosure of future information, no further evaluations should be performed and no additional data should be collected. Vertex may retain and continue to use any data collected before such withdrawal of consent.

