6.3 Randomization

Approximately 490 subjects (245 per arm) who meet eligibility criteria will be stratified by age at Screening Visit (<18 versus \geq 18 years of age), sex (male versus female), and percent predicted FEV₁ severity determined during the Screening Period (<70 versus \geq 70), and then randomized (1:1) to either TEZ/IVA or placebo. An interactive web response system (IWRS) will be used for randomization following a list of randomization codes generated by a designated vendor [REDACTED].

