8.3.2.1 Definition of Secondary Efficacy Endpoints

8.3.2.1.1 Key Secondary Efficacy Endpoints

Relative change in percent predicted FEV₁ from baseline through Week 24

The calculations of percent predicted FEV₁ and the relative change from baseline at each post baseline visit will follow the definitions in Section 8.3.1.1 and Section 8.1.

Number of pulmonary exacerbations through Week 24

The pulmonary exacerbation (PEX) analysis period will start from the first dose of study drug and end on the last efficacy assessment up to Week 24.

Pulmonary exacerbation: A pulmonary exacerbation is defined as a new event or change in antibiotic therapy (IV, inhaled, or oral) for any 4 or more of the following signs/symptoms:

- Change in sputum
- New or increased hemoptysis

- Increased cough
- Increased dyspnea
- Malaise, fatigue, or lethargy
- Temperature above 38°C (equivalent to approximately 100.4°F)
- Anorexia or weight loss
- Sinus pain or tenderness
- Change in sinus discharge
- Change in physical examination (PE) of the chest
- Decrease in pulmonary function by 10%
- Radiographic changes indicative of pulmonary infection

The number of pulmonary exacerbations through Week 24 will be analyzed by comparing the *annualized number of pulmonary exacerbations* for each treatment group. It will be calculated as

$$48 \times (\text{total number of pulmonary exacerbations}) / (\text{total duration of post-baseline assessment in weeks}),$$

where total number of pulmonary exacerbations and total duration of post-baseline assessment are obtained from all subjects in the same treatment group.

Absolute change from baseline in BMI at Week 24

To calculate absolute change from baseline in BMI at Week 24, BMI will be calculated as:

$$\text{BMI} = \text{Weight (kg)} / (\text{height [m}^2\text{)})$$

Absolute change from baseline in CFQ-R respiratory domain through Week 24

The absolute change from baseline in the respiratory domain of the CFQ-R (Pooled 'Children Ages 12 and 13' Version and 'Adolescents and Adults' Version) through Week 24 will be analyzed based on the *CFQ-R scaled scores*, as elaborated below.

The CFQ-R^{5,6,7} is a valid CF-specific instrument that measures quality-of-life domains. This study uses three different versions of CFQ-R forms in this study:

- CFQ-R for Children Ages 12 and 13 has a total of 35 questions to form 8 domains. All questions are scored 1, 2, 3, or 4.

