8.3.2.2 Analysis of Secondary Efficacy Endpoints

8.3.2.2.1 Analysis of Key Secondary Efficacy Endpoints

Relative change from baseline in ppFEV₁ through Week 24

Analysis for the relative change from baseline in ppFEV₁ through Week 24 will be similar to that for the primary analysis. The LS Mean (SE) of the overall treatment difference between TEZ/IVA and placebo in the relative change from baseline in percent predicted FEV₁ from Day 15 through Week 24 will be presented along with the 95% confidence interval and a 2-sided *P* value.

The LS Mean (SE) of within-treatment group relative change from baseline at each post-baseline visit along with the corresponding 95% CI and p-value will be estimated from the same MMRM model. The LS Mean (SE) of the treatment difference between TEZ/IVA and placebo at each post-baseline visit will be provided along with the corresponding 95% CI and p-value. The LS means (with 95% CI) at each post-baseline visit will also be plotted by treatment group. Summary statistics of raw values and absolute change from baseline in ppFEV₁ at each visit will be presented. The cumulative distribution of the average relative change from study baseline in ppFEV₁ through week 24 will be plotted by treatment group.

Number of pulmonary exacerbations through Week 24

A negative binomial generalized linear model will be used to compare the rates of pulmonary exacerbations over the 24-week treatment period for the two treatment groups. The estimated rate ratio and the associated 95% CI and p-value will be provided. In this model, the dependent variable will be the number of pulmonary exacerbations through Week 24, (including both on treatment events and events after treatment discontinuation). Treatment, sex, age group at screening (<18 vs. ≥ 18 years old), and baseline percent predicted FEV₁ will be included as covariates. The log of time spent in the study will be treated as the offset in this model. A log link function will be used in this model. If the model does not converge, the negative binomial regression model will be replaced with a Poisson regression model with the same covariates, offset variable, and link function.

Absolute change in BMI from baseline at Week 24

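### The rate of days hospitalized for exacerbation divides an unrestricted count by on-treatment weeks only, although hospitalizations are collected to Week 24 after treatment stops

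*Protocol*

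**What the plan says.** The footnote to the list of exacerbation measures in Protocol 11.6.12.1 gives the numerator as "48 weeks times the total numbers of days in hospital for pulmonary exacerbation" and has it "divided by the total number of weeks on-treatment, for all subjects in the same treatment group". It states no period for the hospital days.

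Protocol 8.1.2 says that subjects who stop study drug early "will remain in the study from the time of discontinuation of study drug treatment through the Week 24 Visit". Protocol 8.1.4 adds that hospitalizations and exacerbations go on being collected from them. Footnote y of Protocol Table 3-2 extends collection of antibiotic therapy for sinopulmonary signs and symptoms, which is needed to classify an exacerbation, to Week 24 for these subjects.

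The SAP treats the closely related exacerbation rate differently. SAP 8.3.2.1.1 uses the same 48-week multiplier but divides by "total duration of post-baseline assessment in weeks". SAP 8.3.2.2.1 counts exacerbations "including both on treatment events and events after treatment discontinuation", with log time in the study as the offset. The visible SAP has no formula for hospital days.

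**The concern.** A rate needs its events and its time at risk to cover the same period. Here the time stops with treatment, but nothing stops the count there, and the data collection ensures that later hospital days will be in the database. A programmer following the footnote literally would include them.

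Two things are at stake. The rate in each arm would be too high. If the arms differ in how much off-treatment follow-up they accumulate, the comparison would also be distorted. In addition, exacerbation counts and the hospital days for those same exacerbations would be reported on different time bases, although both carry the same 48-week scaling and would be read side by side.

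**Working it through.** The documents give no expected hospital-day rate, so there is no figure of the plan's own to reproduce. The check is person-time algebra.

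**Inputs from the documents.** There are 245 subjects per arm (SAP 6.3). "The Treatment Period will last approximately 24 weeks" (Protocol 8.1.2). Protocol 12.1 assumes 10% dropout for sample size, but this is not a treatment-discontinuation rate and is not given by arm.

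**Assumptions.** A fraction *d* of an arm stops treatment at Week *t*, and everyone is followed to Week 24. The values of *d* and *t* are illustrative.

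**Formula.** Let H be all hospital days for exacerbation, and let T_on and T_off be on-treatment and off-treatment follow-up weeks.

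- Rate as written: 48 × H / T_on
- Matched rate: 48 × H / (T_on + T_off)
- Overstatement factor: (T_on + T_off) / T_on = 24 / [(1 − d) × 24 + d × t]

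H cancels, so the factor relative to the matched rate does not depend on whether hospital days are more frequent on or off drug.

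**Overstatement factor (on-treatment weeks per subject in brackets).**

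| Stopping | Week 4 | Week 12 | Week 20 |
|---|---|---|---|
| 5% | 1.043 (23.0) | 1.026 (23.4) | 1.008 (23.8) |
| 10% | 1.091 (22.0) | 1.053 (22.8) | 1.017 (23.6) |

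**Worked case.** Take 245 subjects with 10% stopping at Week 12, and an assumed true rate of 2 hospital days per 48 weeks.

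- T_on = 245 × 22.8 = 5586 weeks
- T_on + T_off = 245 × 24 = 5880 weeks
- H = 2 × 5880 / 48 = 245 days
- Rate as written = 48 × 245 / 5586 = 2.105
- Matched rate = 48 × 245 / 5880 = 2.000

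The overstatement is 5.3%.

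**Between-arm ratio when the true rates are equal, stopping at Week 12.**

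- 5% versus 10%: 22.8 / 23.4 = 0.974
- 5% versus 20%: on-treatment weeks at 20% are 0.8 × 24 + 0.2 × 12 = 21.6, so 21.6 / 23.4 = 0.923
- 10% versus 10%: 1.000

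**What drives the bias.** It is off-treatment follow-up time relative to on-treatment time, not the number who stop. With 10% stopping at Week 20 the factor is 24 / 23.6 = 1.017. With 6% stopping at Week 4, on-treatment weeks are 0.94 × 24 + 0.06 × 4 = 22.8 and the factor is 1.053, so the arm with fewer discontinuations is overstated more. If those who stop also leave the study, T_off is zero and the factor is 1.000.

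**The case against.** The strongest reply is that the mismatch is inferred. The footnote does not say that off-treatment hospital days enter the numerator, and collecting data is not the same as counting them. The SAP itself runs an on-treatment FEV₁ analysis on data collected to Week 24, and its explicit inclusion of later events concerns exacerbation counts only. Nor does the footnote define on-treatment weeks. The study-duration text of the Protocol synopsis treats early discontinuers as able to complete the Treatment Period, so the phrase might mean the whole 24 weeks.

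These readings are possible but do not rescue the wording. Protocol 12.3.2.4 measures duration of treatment from the first to the last day of study drug. When the SAP wants on-treatment data only (SAP 8.3.2.2.3), it says so. Even if either reading was intended, the footnote would need rewording.

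The objection about what is hidden does stand. The SAP prevails over the protocol where methods differ (SAP 3). Its efficacy section has redacted blocks, and SAP Table 11-10 sets display precision for normalized days with exacerbations, a variable that the visible text never defines. A matched formula may exist there, or in the separate document that the SAP foresees for exploratory endpoints.

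A reader might also infer that the arm with more discontinuations is always overstated more. The documents do not support that: timing and continued follow-up matter as much as the count, and no discontinuation rate by arm is given.

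**Conclusion.** The formula as it stands in the protocol is mismatched and should be corrected, but this is a minor point. For 5% to 10% stopping between Weeks 4 and 20 with full follow-up to Week 24, the overstatement is about 1% to 9%. That range rests on assumed discontinuation and on complete follow-up. The ratio between arms is biased only if their shares of off-treatment follow-up differ, and the documents do not say which arm that would disfavour.

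It would be tempting to read this as a threat to the trial's efficacy conclusions, or as proof that the executed analysis was biased. Neither follows. Hospital days for exacerbation are not among the visible primary, key secondary or other secondary endpoints and lie outside the testing hierarchy. The footnote describes a pooled rate per arm and specifies no test. The operative SAP definition, if there is one, cannot be seen.

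**What to change.** In the footnote to Protocol 11.6.12.1, and in any SAP definition of this measure, replace the on-treatment weeks with total weeks of post-baseline assessment, running from first dose to the final efficacy assessment no later than Week 24. This is the basis that SAP 8.3.2.1.1 uses for the exacerbation rate. It keeps all randomized follow-up and puts counts and hospital days on one time scale.

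If an on-treatment rate is what is wanted, keep the denominator and limit the numerator to hospital days on treatment. That is equally coherent but answers a different question, so the choice should be stated.

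Either change costs one phrase and needs no new data collection. If redacted SAP text already gives a matched definition, a cross-reference from the footnote is enough.
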